**Table 14: Probability of Early Termination for Various Safety Event Rates**

Proportion of Subjects Having DLT	Probability of Early Termination Based Upon DLT Rule a	Proportion of Subjects Having Immune Event	Probability of Early Termination Based on Immune-Related Toxicity a
5%	0.0%	5%	6.4%
10%	0.5%	10%	24.6%
15%	2.3%	15%	50.4%
20%	7.0%	20%	74.4%
25%	16.4%	25%	89.8%
30%	32.0%	30%	97.1%
40%	72.5%	40%	99.9%

a Assumes the interim safety analyses occur when enrollment in the active treatment arm are 8, 19, 30, and 41 subjects. Probability estimated via simulation with 100,000 replications.

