9.6. Interim Analysis

An interim safety analysis is planned for Phase 2 after 16 subjects have been enrolled and treated for 8 weeks, and then approximately every 3 months thereafter. If the following is reported during these reviews, enrollment of subjects would be suspended until the sponsor determined the appropriate course of action and notified IRBs and regulatory authorities:

- $\geq 40\%$ of subjects have experienced an AE \geq Grade 3 that was attributable to the investigational agents.

No formal interim analysis for futility or efficacy is planned for this study.

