Rationale for change: Subjects are no longer required to visit clinic every 2 weeks while on monotherapy epacadostat; therefore, the visit structure was altered once subjects become eligible for monotherapy epacadostat or re-treatment with combination therapy.

14. Section 7.6.1.1, Pharmacokinetic Assessment for Epacadostat

Description of change: In Table 24 (Sample Collection Windows for Pharmacokinetic Assessments for Epacadostat), the window for the 6-hour and optional 8- to 10-hour samples was changed to ± 60 minutes (instead of ± 30 minutes).

Rationale for change: Visit windows were lengthened to allow greater flexibility.

15. Section 9.6, Interim Analysis

Description of change: The interim analysis was modified to evaluate all \geq Grade 3 adverse events attributable to the investigational agents in Phase 2 of the study.

Rationale for change: The revised criteria for evaluation allows for efficient monitoring of safety in a larger sample size.

16. Section 10.1.1.1, Epacadostat

Description of change: The packaging/labeling statement was revised to: All Incyte investigational product labels will be in the local language and will comply with the legal requirements of each country.

Rationale for change: The study will now include ex-US centers; therefore, the language was updated for global compliance.

17. Appendix A, Information Regarding Effectiveness of Contraceptive Methods

Description of change: Appendix A was updated with Clinical Trial Facilitation Group's recommendations related to contraception in clinical studies.

Rationale for change: The study will now include ex-US centers; therefore, the language was updated for global compliance.

18. Incorporation of administrative changes. Other minor, administrative changes have been incorporated throughout the Protocol and are noted in the redline version of the amendment.

Amendment 4 (12 JAN 2016)

Overall Rationale for the Amendment:

The primary purpose of this amendment is to modify the tumor types that will be evaluated in the Phase 2 portion of the study.

This amendment includes the changes to INCB 24360-203 Protocol Amendment 3 (10 JUL 2015) summarized below.

1. **Synopsis; Section 1, Introduction; Section 3, Subject Eligibility; Section 4.1, Overall Study Design; Section 4.4, Number of Subjects; Section 9.2.2, Sample Size for Phase 2**

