## **2. STUDY INFORMATION, OBJECTIVES, AND ENDPOINTS**

### **2.1. Protocol and Case Report Form Version**

This SAP is based on INCB 24360-203 Protocol Amendment 1 dated 29 SEP 2014 and case report form (CRF) approved on 08 SEP 2014. Unless superseded by an amendment, this SAP will be effective for all subsequent Protocol amendments and CRF versions.

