## 5. STATISTICAL METHODOLOGY

### 5.1. General Methodology

Unless otherwise noted, SAS® software (SAS Institute Inc, Cary, NC; version 9.1 or later) will be used for the generation of all tables, graphs, and statistical analyses. Descriptive summaries for continuous variables will include, but not be limited to, the number of observations, mean, standard deviation, median, minimum, and maximum. Descriptive summaries for categorical variables will include the number and percentage of subjects in each category.

For the dose-escalation portion of the study, the Phase 1 safety population (defined in [Section 5.3.2](#)) will be used for all safety analyses, and the Phase 1 intent-to-treat (ITT) population will be used for all efficacy analyses. For the expansion portion of the study, the Phase 2 safety population will be used for all safety analyses, and the Phase 2 ITT population will be used for all efficacy analyses. Analyses of PK endpoints are described in [Section 7.5](#) and will be performed by the Incyte and MedImmune pharmacokineticist, respectively.

Interim safety analyses are planned for this study as defined in [Section 9](#).

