### 9.2. Guidelines for Decision Rules

An interim safety analysis is planned for Phase 2 after 16 subjects have been enrolled and treated for 8 weeks, and then every 3 months thereafter. If either of the following is reported during

these reviews, enrollment of subjects would be suspended until the sponsor determined the appropriate course of action and notified IRBs and regulatory authorities:

- $\geq 40\%$  of subjects report a DLT or
- $\geq 20\%$  of subjects have had a nondermatologic immune-related AE  $\geq$  Grade 3 that was attributable to the investigational agent.

Based on these rules, the probabilities of stopping a treatment group for safety is provided in [Table 14](#).

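### SAP 9.2 keeps a Phase 2 suspension rule that conflicts with current Protocol 9.6, and Table 14's look sizes are not reconciled with the stated first look at 16 subjects

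*SAP*

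**What the plan says.** **SAP 9.2.** "An interim safety analysis is planned for Phase 2 after 16 subjects have been enrolled and treated for 8 weeks", with reviews every 3 months after that. Enrolment is suspended if at least 40% of subjects report a DLT, or if at least 20% "of subjects have had a nondermatologic immune-related AE" of Grade 3 or higher attributed to the investigational agent. The section then says: "Based on these rules, the probabilities of stopping a treatment group for safety is provided in" Table 14. The footnote to that table reads: "Assumes the interim safety analyses occur when enrollment in the active treatment arm are 8, 19, 30, and 41 subjects".

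**Protocol 9.6 (current).** The first review is at the same point and reviews follow about every 3 months, but there is one criterion: at least 40% "of subjects have experienced an AE" of Grade 3 or higher attributed to the investigational agents. Appendix E, Amendment 5, item 15 records the change and gives the reason: "The revised criteria for evaluation allows for efficient monitoring of safety in a larger sample size".

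**Status of the SAP.** It was written against Protocol Amendment 1. Section 5.1 says "Interim safety analyses are planned for this study as defined in" Section 9. Section 2.1 says "Unless superseded by an amendment, this SAP will be effective for all subsequent Protocol amendments and CRF versions". Table 15 lists only the original version of 26 NOV 2014.

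**The concern.** This is the only numerical stopping criterion for Phase 2 safety in either document, and the study has no external data monitoring committee (Protocol 8.7). Sites are bound to the Protocol (11.3), while SAP 5.1 sends the analyst to SAP Section 9. At the same review the two would count different events against different limits.

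The DLT limb has a further difficulty. Protocol 5.5.1 places DLT evaluation in dose escalation and does not say that DLTs are assessed in Phase 2.

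Table 14 is the only statement of how the rule behaves. A reader would use it to judge how often enrolment would be halted needlessly and how reliably a real problem would be caught. It can serve neither purpose if it describes a replaced rule at look sizes that do not correspond to the stated schedule.

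**Working it through.** **1. Trigger counts at the first review (n = 16).** A limb triggers at the smallest whole number at or above threshold × n.

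- SAP immune limb: 0.20 × 16 = 3.2, so 4 events.
- SAP DLT limb: 0.40 × 16 = 6.4, so 7 events.
- Protocol 9.6: 0.40 × 16 = 6.4, so 7 events.

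**2. Where the rules disagree at n = 16.**

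| Subjects with events, of 16 | SAP 9.2 | Protocol 9.6 |
|---|---|---|
| 4, 5 or 6 with a related nondermatologic immune AE of Grade ≥3; no other related Grade ≥3 AE; fewer than 7 DLTs | Suspend | Continue |
| 7 with a related Grade ≥3 AE, none immune and none a DLT | Continue | Suspend |

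Neither rule contains the other.

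**3. Reproducing Table 14.** The method is an exact sequential binomial: at each look of n subjects, stop if events/n is at or above the threshold; otherwise carry the distribution of counts to the next look. With looks at 8, 19, 30 and 41:

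| True rate | 5% | 10% | 15% | 20% | 25% | 30% | 40% |
|---|---|---|---|---|---|---|---|
| Immune limb, Table 14 | 6.4 | 24.6 | 50.4 | 74.4 | 89.8 | 97.1 | 99.9 |
| Immune limb, exact | 6.3 | 24.6 | 50.5 | 74.6 | 90.0 | 97.0 | 99.9 |
| DLT limb, Table 14 | 0.0 | 0.5 | 2.3 | 7.0 | 16.4 | 32.0 | 72.5 |
| DLT limb, exact | 0.0 | 0.5 | 2.4 | 7.1 | 16.6 | 32.2 | 72.4 |

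All 14 cells agree within 0.2 points. The table is computed correctly for its footnote, with a first look at 8.

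**4. First look only, immune limb.** This needs no assumption about later looks. It does assume that the threshold is applied to 16 subjects. At n = 8 the limb triggers at 2 events (0.20 × 8 = 1.6); at n = 16 it triggers at 4.

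- 5% true rate: P(Bin(8, 0.05) ≥ 2) = 5.7%; P(Bin(16, 0.05) ≥ 4) = 0.7%.
- 10% true rate: P(Bin(8, 0.10) ≥ 2) = 18.7%; P(Bin(16, 0.10) ≥ 4) = 6.8%.

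**5. Whole schedule, immune limb.** Neither document gives accrual per 3 months, so every later look here is an assumption.

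| Looks | 5% | 10% | 15% | 20% |
|---|---|---|---|---|
| Table 14 (8/19/30/41) | 6.4 | 24.6 | 50.4 | 74.4 |
| 16/19/30/41, one arm | 1.4 | 13.9 | 40.0 | 68.1 |
| 16/27/38/41, one arm | 0.8 | 9.6 | 33.2 | 62.7 |
| 4/12/20/30/41, one arm | 19.5 | 40.8 | 63.3 | 81.8 |

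The last row takes 16 as a pooled count spread equally over the SAP's four tumour cohorts (16/4 = 4), with the percentage applied within each arm.

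The pooled total also matters. At a 20% true rate, schedules ending at 68, the lower end of the SAP's 68 to 157 Phase 2 subjects (16/42/68 and 16/30/50/68), give 66.2% to 73.2%. Six schedules ending at the current Protocol's 140 or 192 give 76.6% to 83.3%. Table 14's 74.4% lies between the two ranges.

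**The case against.** The strongest reply concerns the units. SAP 9.2 introduces Table 14 as the chance of stopping a treatment group, and the footnote counts subjects in one arm, whereas the 16 is a count for Phase 2. If 16 is pooled, an arm would usually hold fewer than 16 at the first review, so 8 is possible and the footnote openly calls it an assumption. This stands as far as it goes. A reader might infer that Table 14 was run with a wrong input, but the documents do not establish that. They show an unexplained unit.

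A reader might also infer that Table 14 overstates the chance of suspension. That holds at low rates if the threshold is applied at 16. It reverses if the percentage is applied per arm at small first looks: 19.5% against 6.4% at a 5% true rate in the schedule above. The documents do not settle which applies. Amendment 5's mention of a larger sample leans towards pooling in the current Protocol. The SAP's own Stage 1 sizes (15, 16, 21 and 16) would let three of its four cohorts reach 16 on their own.

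Nor is the SAP rule simply the stricter one. Only its immune limb has a lower threshold, and the second row of the disagreement table runs the other way.

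On the rule conflict, it can be said that an old SAP is expected to lag, that an original version naturally lists only itself, and that the amendment able to supersede it under SAP 2.1 could be a Protocol amendment. The last reading is possible but not stated, and the sentence makes the SAP effective for subsequent Protocol amendments. Practical harm is limited: sites follow the Protocol, crossing a limit only pauses enrolment pending the sponsor's decision, and sponsor and investigators confer about weekly (Protocol 8.7). Table 14 feeds no estimate, interval or sample size.

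**Conclusion.** The conflict between the two suspension rules is established on the text. It has consequences in both directions at the first review: 4 to 6 qualifying immune events suspend under the SAP only, and 7 qualifying non-immune events suspend under the Protocol only. That the SAP rule is the older one follows from its date, its Amendment 1 basis and the Amendment 5 entry; the full earlier Protocol wording is not in the documents.

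For Table 14, three things are established: it is arithmetically sound for looks at 8/19/30/41, the SAP does not connect those looks to a first review at 16, and the table does not describe the rule in current Protocol 9.6. The size of any discrepancy is conditional. With the threshold applied at 16, the first-look immune-limb probability is 0.7% rather than 5.7% at a 5% true rate, and 6.8% rather than 18.7% at 10%. Beyond the first look, size and direction depend on assumed later looks and on pooled or per-arm counting. This should be corrected, but it does not affect the efficacy analysis.

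**What to change.** - Replace the SAP 9.2 criteria with the single Protocol 9.6 criterion, dropping both the DLT and the immune limbs.
- State in both documents whether the 16 subjects and the 40% are pooled over Phase 2 or taken per cohort.
- Recompute Table 14 for that rule and unit, with look sizes based on expected accrual per 3 months and printed in the footnote.

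As a guide to the pooled result, the 40% limit was run over six assumed schedules: 16/50/90/140; 16/40/70/100/140; 16/30/50/70/90/110/140; 16/60/110/160/192; 16/46/76/106/136/166/192; and 16 then every 11 to 192. The probability of suspension is 2.7–3.2% at a 20% true rate of related Grade ≥3 AEs, 8.3–10.6% at 25%, 20.8–26.7% at 30%, 78.6–85.1% at 40% and 99.8–100.0% at 50%.

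The cost is a SAP amendment, one clarifying phrase in the Protocol and a short recalculation. No trial procedure or sample size changes, though some stated probabilities may look less favourable.

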## 10. CHANGES AND MODIFICATIONS TO THE ANALYSIS PLAN

Dates for the SAP, including any amendments, are included in [Table 15](#).

**Table 15: Dates for SAP Amendments**

SAP Version	Date
Original	26 NOV 2014

### 10.1. Changes to Protocol-Defined Analyses

Not applicable.

### 10.2. Changes to the Statistical Analysis Plan

Not applicable.

## APPENDIX A. LABORATORY TESTS: REQUIRED ANALYTES AND PULMONARY FUNCTION TESTS

Comprehensive Chemistry Panel	Hematology	Other
Albumin Alkaline phosphatase ALT AST Amylase Bicarbonate Blood urea nitrogen Calcium Chloride Creatinine Glucose Iron Lactate dehydrogenase Lipase Phosphorus Potassium Sodium Total bilirubin Direct bilirubin (if total bilirubin is elevated above ULN) Total protein Uric acid	Complete blood count including: Hemoglobin Hematocrit Platelet count Red blood cell count White blood cell count Differential count including: 
 
• Basophils
 
• Eosinophils
 
• Lymphocytes
 
• Monocytes
 
• Neutrophils
 
	Serology: Hepatitis B surface antigen Hepatitis B surface antigen antibody Hepatitis B core antibody Hepatitis C virus antibody HCV-RNA HBV-DNA  Pregnancy test: Female subjects of childbearing potential only require a serum test at screening. Pregnancy tests (serum or urine) should be repeated if required by local regulations.  Urinalysis with microscopic examination: Color and appearance pH and specific gravity Bilirubin Glucose Ketones Leukocytes Nitrite Occult blood Protein Urobilinogen  Coagulation: PT aPTT INR
Endocrine Monitoring	Standard LFT Monitoring	
Adrenocorticotrophic hormone Serum cortisol (9 AM) Luteinizing hormone a Prolactin Thyroid stimulating hormone Free thyroxine (T4) Total triiodothyronine (T3) Serum testosterone (9 AM) b	Alkaline phosphatase ALT AST Total bilirubin	
Pulmonary Function Tests		
Largest FVC FVC % Predicted Largest FEV 1 FEV 1 % predicted FEV 1 /FVC FEF 25-75% FEF 25-75% Predicted Peak expiratory flow	Pulse Oximetry Oxygen saturation Pulse rate	DLCO DLCO DLCO % predicted DLCO/VA DLCO/VA % predicted DLCO corrected for Hb DLCO corrected % predicted DLCO/VA corrected for Hgb DLCO/VA corrected % predicted

ALT = alanine aminotransferase; aPTT = activated partial thromboplastin time; AST = aspartate aminotransferase; DLCO = diffusing capacity of the lung for carbon monoxide; FEF = forced expiratory flow; FEV1 = forced expiratory volume in 1 second; FVC = forced vital capacity; HBV-DNA = hepatitis B virus deoxyribonucleic acid; HCV-RNA = hepatitis C virus ribonucleic acid; INR = international normalized ratio; LFT = liver function test; PT = prothrombin time; ULN = upper limit of normal; VA = alveolar volume.

a Not needed in subjects taking thyroid hormone replacement therapy.

b Not needed in women, surgically castrated men, or men taking luteinizing hormone-releasing hormone agonist therapy.

## APPENDIX B. LABORATORY GRADING

Laboratory	Grade 1	Grade 2	Grade 3	Grade 4
Haptoglobin decreased	< LLN	–	–	–
Hemoglobin decreased	< LLN - 100 g/L	< 100 – 80 g/L	< 80 g/L	–
Hemoglobin increased	Increase in > 0 – 2 g/dL above ULN or above baseline if baseline is above ULN	Increase in > 2 – 4 g/dL above ULN or above baseline if baseline is above ULN	Increase in > 4 g/dL above ULN or above baseline if baseline is above ULN	–
Lymphocyte count decreased	< LLN – $0.8 \times 10^9$ /L	< $0.8 - 0.5 \times 10^9$ /L	< $0.5 - 0.2 \times 10^9$ /L	< $0.2 \times 10^9$ /L
Lymphocyte count increased	-	> $4000/\text{mm}^3 - 20,000/\text{mm}^3$	> $20,000/\text{mm}^3$	–
Neutrophil count decreased	< LLN – $1.5 \times 10^9$ /L	< $1.5 - 1.0 \times 10^9$ /L	< $1.0 - 0.5 \times 10^9$ /L	< $0.5 \times 10^9$ /L
Platelet count decreased	< LLN - $75.0 \times 10^9$ /L	< $75.0 - 50.0 \times 10^9$ /L	< $50.0 - 25.0 \times 10^9$ /L	< $25.0 \times 10^9$ /L
White blood cell decreased	< LLN – $3.0 \times 10^9$ /L	< $3.0 - 2.0 \times 10^9$ /L	< $2.0 - 1.0 \times 10^9$ /L	< $1.0 \times 10^9$ /L
Activated partial thromboplastin time prolonged	> ULN – $1.5 \times$ ULN	> $1.5 - 2.5 \times$ ULN	> $2.5 \times$ ULN	–
INR increased	> 1 - $1.5 \times$ ULN	> $1.5 - 2.5 \times$ ULN	> $2.5 \times$ ULN;	–
Alanine aminotransferase increased	> ULN – $3.0 \times$ ULN	> $3.0 - 5.0 \times$ ULN	> $5.0 - 20.0 \times$ ULN	> $20.0 \times$ ULN
Alkaline phosphatase increased	> ULN – $2.5 \times$ ULN	> $2.5 - 5.0 \times$ ULN	> $5.0 - 20.0 \times$ ULN	> $20.0 \times$ ULN
Aspartate aminotransferase increased	> ULN – $3.0 \times$ ULN	> $3.0 - 5.0 \times$ ULN	> $5.0 - 20.0 \times$ ULN	> $20.0 \times$ ULN
Blood bilirubin increased	> ULN - $1.5 \times$ ULN	> $1.5 - 3.0 \times$ ULN	> $3.0 - 10.0 \times$ ULN	> $10.0 \times$ ULN
CD4 lymphocytes decreased	< LLN - $0.5 \times 10^9$ /L	< $0.5 - 0.2 \times 10^9$ /L	< $0.2 - 0.05 \times 10^9$ /L	< $0.05 \times 10^9$ /L
Cholesterol high	> ULN - 7.75 mmol/L	> 7.75 - 10.34 mmol/L	> 10.34 - 12.92 mmol/L	> 12.92 mmol/L
CPK increased	> ULN - $2.5 \times$ ULN	> $2.5 \times$ ULN - $5 \times$ ULN	> $5 \times$ ULN - $10 \times$ ULN	> $10 \times$ ULN
Creatinine increased	> 1 - $1.5 \times$ baseline; >ULN - $1.5 \times$ ULN	> $1.5 - 3.0 \times$ baseline; > $1.5 - 3.0 \times$ ULN	> 3.0 baseline; > $3.0 - 6.0 \times$ ULN	> $6.0 \times$ ULN

Laboratory	Grade 1	Grade 2	Grade 3	Grade 4
Fibrinogen decreased	< 1.0 - 0.75 × LLN or < 25% decrease from baseline	< 0.75 - 0.5 × LLN or 25 - < 50% decrease from baseline	< 0.5 - 0.25 × LLN or 50 - < 75% decrease from baseline	< 0.25 × LLN or 75% decrease from baseline or absolute value < 50 mg/dL
GGT increased	> ULN - 2.5 × ULN	> 2.5 - 5.0 × ULN	> 5.0 - 20.0 × ULN	> 20.0 × ULN
Lipase increased	> ULN - 1.5 × ULN	> 1.5 - 2.0 × ULN	> 2.0 - 5.0 × ULN	> 5.0 × ULN
Serum amylase increased	> ULN - 1.5 × ULN	> 1.5 - 2.0 × ULN	> 2.0 - 5.0 × ULN	> 5.0 × ULN
Serum albumin decreased	< LLN - 30 g/L	< 30 - 20 g/L	< 20 g/L	–
Serum calcium decreased	< LLN - 2.0 mmol/L	< 2.0 - 1.75 mmol/L	< 1.75 - 1.5 mmol/L	< 1.5 mmol/L
Serum calcium increased	> ULN - 2.9 mmol/L	> 2.9 - 3.1 mmol/L	> 3.1 - 3.4 mmol/L	> 3.4 mmol/L
Serum glucose decreased (fasting)	< LLN - 3.0 mmol/L	< 3.0 - 2.2 mmol/L	< 2.2 - 1.7 mmol/L	< 1.7 mmol/L
Serum glucose increased (fasting)	> ULN - 8.9 mmol/L	> 8.9 - 13.9 mmol/L	> 13.9 - 27.8 mmol/L	> 27.8 mmol/L
Serum magnesium decreased	< LLN - 0.5 mmol/L	< 0.5 - 0.4 mmol/L	< 0.4 - 0.3 mmol/L	< 0.3 mmol/L
Serum magnesium increased	> ULN - 1.23 mmol/L	–	> 1.23 - 3.30 mmol/L	> 3.30 mmol/L
Serum phosphate decreased	< LLN - 0.8 mmol/L	< 0.8 - 0.6 mmol/L	< 0.6 - 0.3 mmol/L	< 0.3 mmol/L
Serum potassium decreased	< LLN - 3.0 mmol/L	–	< 3.0 - 2.5 mmol/L	< 2.5 mmol/L
Serum potassium increased	> ULN - 5.5 mmol/L	> 5.5 - 6.0 mmol/L	> 6.0 - 7.0 mmol/L	> 7.0 mmol/L
Serum sodium decreased	< LLN - 130 mmol/L	–	< 130 - 120 mmol/L	< 120 mmol/L
Serum sodium increased	> ULN - 150 mmol/L	> 150 - 155 mmol/L	> 155 - 160 mmol/L	> 160 mmol/L
Serum triglycerides increased	1.71 - 3.42 mmol/L	> 3.42 - 5.7 mmol/L	> 5.7 - 11.4 mmol/L	> 11.4 mmol/L
Serum uric acid increased	> ULN - 0.59 mmol/L	–	> ULN - 0.59 mmol/L	> 0.59 mmol/L;

## APPENDIX C. PLANNED TABLES, FIGURES, AND LISTINGS

This appendix provides a list of the planned tables, figures, and listings for the CSR. Standard tables will follow the conventions in the Standard Safety Tables initial version. Shells are provided for nonstandard, in-text CSR tables. In-text tables are identical in structure and content as appendix tables, but follow a Rich Text Format.

### Tables

Table No.	Title	Population	Standard	In-Text
Baseline and Demographic Characteristics				
1.1.1	Analysis Populations		X	X
1.1.2.1	Summary of Subject Disposition	Phase 1 ITT	X	X
1.1.2.2	Summary of Subject Disposition	Phase 2 ITT	X	X
1.2.1.1	Summary of Demographics	Phase 1 ITT	X	X
1.2.1.2	Summary of Demographics	Phase 2 ITT	X	X
1.3.1.1	Summary of Baseline Disease Characteristics	Phase 1 ITT		X
1.3.1.2	Summary of Baseline Disease Characteristics	Phase 2 ITT		X
1.3.2.1	Summary of General Medical History	Phase 1 ITT		
1.3.2.2	Summary of General Medical History	Phase 2 ITT		
1.4.1.1	Summary of Prior Medications	Phase 1 ITT		
1.4.1.2	Summary of Prior Medications	Phase 2 ITT		
1.4.2.1	Summary of Concomitant Medications	Phase 1 ITT		
1.4.2.2	Summary of Concomitant Medications	Phase 2 ITT		
1.4.3.1	Summary of Prior Medications for Cancer	Phase 1 ITT		X
1.4.3.2	Summary of Prior Medications for Cancer	Phase 2 ITT		X
1.5.1	Summary of Study Medication Compliance	Phase 1 Safety		X
1.5.2	Summary of Study Medication Compliance	Phase 2 Safety		X
Efficacy				
2.1.1	Kaplan-Meier Analysis of Progression-Free Survival by RECIST Criteria	Phase 1 ITT		X
2.1.2	Kaplan-Meier Analysis of Progression-Free Survival by RECIST Criteria	Phase 2 ITT		X
2.2.1.1	Summary of Best Response by RECIST Criteria	Phase 1 ITT		X
2.2.1.2	Summary of Best Response by RECIST Criteria	Phase 2 ITT		X
2.2.4.1	Summary of Duration of Response	Phase 1 ITT		X
2.2.4.2	Summary of Duration of Response	Phase 2 ITT		X
Safety				
3.1.1.1	Summary of Exposure and Duration of Exposure to INCB024360 and MEDI4736	Phase 1 ITT		X
3.1.1.2	Summary of Exposure and Duration of Exposure to INCB024360 and MEDI4736	Phase 2 ITT		X
3.2.1.1	Overall Summary of Treatment-Emergent Adverse Events	Phase 1 Safety	X	X
3.2.1.2	Overall Summary of Treatment-Emergent Adverse Events	Phase 2 Safety	X	X
3.2.2.1	Summary of Treatment-Emergent Adverse Events By MedDRA System Organ Class and Preferred Term	Phase 1 Safety	X	

Table No.	Title	Population	Standard	In-Text
3.2.2.2	Summary of Treatment-Emergent Adverse Events By MedDRA System Organ Class and Preferred Term	Phase 2 Safety	X	
3.2.3.1	Summary of Treatment-Emergent Adverse Events By MedDRA Preferred Term in Decreasing Order of Frequency	Phase 1 Safety	X	X
3.2.3.2	Summary of Treatment-Emergent Adverse Events By MedDRA Preferred Term in Decreasing Order of Frequency	Phase 2 Safety	X	X
3.2.4.1	Summary of Treatment-Emergent Adverse Events By MedDRA System Organ Class, Preferred Term, and Maximum Severity	Phase 1 Safety	X	
3.2.4.2	Summary of Treatment-Emergent Adverse Events By MedDRA System Organ Class, Preferred Term, and Maximum Severity	Phase 2 Safety	X	
3.2.7.1	Summary of Grade 3 or Higher Treatment-Emergent Adverse Events By MedDRA System Organ Class and Preferred Term	Phase 1 Safety	X	X
3.2.7.2	Summary of Grade 3 or Higher Treatment-Emergent Adverse Events By MedDRA System Organ Class and Preferred Term	Phase 2 Safety	X	X
3.2.11.1	Summary of Treatment-Related Adverse Events By MedDRA System Organ Class and Preferred Term	Phase 1 Safety	X	
3.2.11.2	Summary of Treatment-Related Adverse Events By MedDRA System Organ Class and Preferred Term	Phase 2 Safety	X	
3.2.12.1	Summary of Treatment-Related Adverse Events By MedDRA Preferred Term in Decreasing Order of Frequency	Phase 1 Safety	X	
3.2.12.2	Summary of Treatment-Related Adverse Events By MedDRA Preferred Term in Decreasing Order of Frequency	Phase 2 Safety	X	
3.2.13.1	Summary of Treatment-Related Adverse Events By MedDRA System Organ Class, Preferred Term, and Maximum Severity	Phase 1 Safety	X	
3.2.13.2	Summary of Treatment-Related Adverse Events By MedDRA System Organ Class, Preferred Term, and Maximum Severity	Phase 2 Safety	X	
3.2.16.1	Summary of Grade 3 or Higher Treatment-Related Adverse Events By MedDRA System Organ Class and Preferred Term	Phase 1 Safety	X	
3.2.16.2	Summary of Grade 3 or Higher Treatment-Related Adverse Events By MedDRA System Organ Class and Preferred Term	Phase 2 Safety	X	
3.2.17.1	Summary of Treatment-Emergent Adverse Events Leading to Death By MedDRA System Organ Class and Preferred Term	Phase 1 Safety	X	X
3.2.17.2	Summary of Treatment-Emergent Adverse Events Leading to Death By MedDRA System Organ Class and Preferred Term	Phase 2 Safety	X	X
3.2.18.1	Summary of Serious Treatment-Emergent Adverse Events By MedDRA System Organ Class and Preferred Term	Phase 1 Safety	X	X
3.2.18.2	Summary of Serious Treatment-Emergent Adverse Events By MedDRA System Organ Class and Preferred Term	Phase 2 Safety	X	X

Table No.	Title	Population	Standard	In-Text
3.2.19.1	Summary of Non-Serious Treatment-Emergent Adverse Events By MedDRA System Organ Class and Preferred Term	Phase 1 Safety	X	
3.2.19.2	Summary of Non-Serious Treatment-Emergent Adverse Events By MedDRA System Organ Class and Preferred Term	Phase 2 Safety	X	
3.2.20.1	Summary of Treatment-Related Serious Adverse Events By MedDRA System Organ Class and Preferred Term	Phase 1 Safety	X	
3.2.20.2	Summary of Treatment-Related Serious Adverse Events By MedDRA System Organ Class and Preferred Term	Phase 2 Safety	X	
3.2.21.1	Summary of Treatment-Emergent Adverse Events Leading to Withdrawal From the Study By MedDRA System Organ Class and Preferred Term	Phase 1 Safety	X	X
3.2.21.2	Summary of Treatment-Emergent Adverse Events Leading to Withdrawal From the Study By MedDRA System Organ Class and Preferred Term	Phase 2 Safety	X	X
3.2.22.1	Summary of Treatment-Emergent Adverse Events Leading to Dose Reduction By MedDRA System Organ Class and Preferred Term	Phase 1 Safety	X	
3.2.22.2	Summary of Treatment-Emergent Adverse Events Leading to Dose Reduction By MedDRA System Organ Class and Preferred Term	Phase 2 Safety	X	
3.2.23.1	Summary of Treatment-Emergent Adverse Events Leading to Discontinuation of Drug Medication By MedDRA System Organ Class and Preferred Term	Phase 1 Safety	X	X
3.2.23.2	Summary of Treatment-Emergent Adverse Events Leading to Discontinuation of Drug Medication By MedDRA System Organ Class and Preferred Term	Phase 2 Safety	X	X
3.2.25.1	Summary of Treatment-Emergent Immune-Related Adverse Events By MedDRA System Organ Class and Preferred Term (Investigator Determined)	Phase 1 Safety	X	X
3.2.25.2	Summary of Treatment-Emergent Immune-Related Adverse Events By MedDRA System Organ Class and Preferred Term (Investigator Determined)	Phase 2 Safety	X	X
3.2.26.1	Summary of Grade 3 or Higher Treatment-Emergent Immune-Related Adverse Events By MedDRA System Organ Class and Preferred Term (Investigator Determined)	Phase 1 Safety	X	X
3.2.26.2	Summary of Grade 3 or Higher Treatment-Emergent Immune-Related Adverse Events By MedDRA System Organ Class and Preferred Term (Investigator Determined)	Phase 2 Safety	X	X
3.2.27.1	Summary of Treatment-Emergent Immune-Related Adverse Events By MedDRA System Organ Class and Preferred Term (With Grade Specific)	Phase 1 Safety	X	X
3.2.27.2	Summary of Treatment-Emergent Immune-Related Adverse Events By MedDRA System Organ Class and Preferred Term (With Grade Specific)	Phase 2 Safety	X	X
3.2.28.1	Summary of Treatment-Emergent Immune-Related Adverse Events By MedDRA System Organ Class and Preferred Term (Regardless of Grade)	Phase 1 Safety	X	X

Table No.	Title	Population	Standard	In-Text
3.2.28.2	Summary of Treatment-Emergent Immune-Related Adverse Events By MedDRA System Organ Class and Preferred Term (Regardless of Grade)	Phase 2 Safety	X	X
3.2.29.1	Summary of Grade 3 or Higher Treatment-Emergent Immune-Related Adverse Events By MedDRA System Organ Class and Preferred Term	Phase 1 Safety	X	X
3.2.29.2	Summary of Grade 3 or Higher Treatment-Emergent Immune-Related Adverse Events By MedDRA System Organ Class and Preferred Term	Phase 2 Safety	X	X
3.2.30.1	Summary of Adverse Events of Special Interest By MedDRA System Organ Class and Preferred Term	Phase 1 Safety	X	X
3.2.30.2	Summary of Adverse Events of Special Interest By MedDRA System Organ Class and Preferred Term	Phase 2 Safety	X	X
Lab				
3.3.1	Summary of Laboratory Values - Hematology	Phase 1 Safety	X	
3.3.2	Summary of Laboratory Values - Hematology	Phase 2 Safety	X	
3.3.3	Summary of Laboratory Values - Chemistry	Phase 1 Safety	X	
3.3.4	Summary of Laboratory Values - Chemistry	Phase 2 Safety	X	
3.3.5.1	Shift Summary of Laboratory Values in CTC Grade - To the Worst Abnormal Value (Tests with One Directional CTC Grade)	Phase 1 Safety	X	X
3.3.5.2	Shift Summary of Laboratory Values in CTC Grade - To the Worst Abnormal Value (Tests with One Directional CTC Grade)	Phase 2 Safety	X	X
3.3.6.1	Shift Summary of Laboratory Values in CTC Grade - To the Worst Abnormal Value (Tests with Two Directional CTC Grade)	Phase 1 Safety	X	
3.3.6.2	Shift Summary of Laboratory Values in CTC Grade - To the Worst Abnormal Value (Tests with Two Directional CTC Grade)	Phase 2 Safety	X	
3.4.1.1	Summary of Systolic Blood Pressure	Phase 1 Safety	X	
3.4.1.2	Summary of Systolic Blood Pressure	Phase 2 Safety	X	
3.4.2.1	Summary of Diastolic Blood Pressure	Phase 1 Safety	X	
3.4.2.2	Summary of Diastolic Blood Pressure	Phase 2 Safety	X	
3.4.3.1	Summary of Heart Rate	Phase 1 Safety	X	
3.4.3.2	Summary of Heart Rate	Phase 2 Safety	X	
3.4.4.1	Summary of Body Temperature	Phase 1 Safety	X	
3.4.4.2	Summary of Body Temperature	Phase 2 Safety	X	
3.4.5.1	Summary of Respiration Rate	Phase 1 Safety	X	
3.4.5.2	Summary of Respiration Rate	Phase 2 Safety	X	
3.4.6.1	Summary of Subjects with Clinically Notable Vital Signs	Phase 1 Safety	X	
3.4.6.2	Summary of Subjects with Clinically Notable Vital Signs	Phase 2 Safety	X	
3.5.1.1	Summary of 12-Lead ECG: PR Interval Values	Phase 1 Safety	X	
3.5.1.2	Summary of 12-Lead ECG: PR Interval Values	Phase 2 Safety	X	
3.5.2.1	Summary of 12-Lead ECG: QRS Interval Values	Phase 1 Safety	X	
3.5.2.2	Summary of 12-Lead ECG: QRS Interval Values	Phase 2 Safety	X	

Table No.	Title	Population	Standard	In-Text
3.5.3.1	Summary of 12-Lead ECG: QT Interval Values	Phase 1 Safety	X	
3.5.3.2	Summary of 12-Lead ECG: QT Interval Values	Phase 2 Safety	X	
3.5.4.1	Summary of 12-Lead ECG: QTcB Interval Values	Phase 1 Safety	X	
3.5.4.2	Summary of 12-Lead ECG: QTcB Interval Values	Phase 2 Safety	X	
3.5.5.1	Summary of 12-Lead ECG: QTcF Interval Values	Phase 1 Safety	X	
3.5.5.2	Summary of 12-Lead ECG: QTcF Interval Values	Phase 2 Safety	X	
3.5.6.1	Summary of 12-Lead ECG: RR Interval Values	Phase 1 Safety	X	
3.5.6.2	Summary of 12-Lead ECG: RR Interval Values	Phase 2 Safety	X	
3.5.7.1	Summary of Treatment Emergent, Clinically Significant ECG Abnormality from Baseline	Phase 1 Safety		X
3.5.7.2	Summary of Clinically Notable ECG Abnormalities	Phase 2 Safety		X

